9.1.1.3. Unanticipated Adverse Device Effect

An Unanticipated Adverse Device Effect (UADE) is defined as any serious adverse effect on the health or safety or any life-threatening problem or death caused by, or associated with, a device, if that effect, problem, or death was not previously identified in nature, severity, or degree of incidence in the investigational plan or application (including a supplementary plan or application), or any other unanticipated serious problem associated with a device that relates to the rights, safety, or welfare of subjects. An AE will be counted as an *unanticipated adverse device effect* if the Principal Investigator answered Z8@M[ĀNIĀNOMĀRIGĀ,Z7[ĀIHĀNC@Ā-0Ā eCRF.

9.1.2. Safety Measures

Table 3 lists the measures to be evaluated for this study.

Table 3: Safety Assessments

Safety Measures	Note
Slit Lamp Exam	Slit-lamp examinations will be performed with anterior chamber cells, anterior chamber flare being graded on a standardized scaling as listed in Section 9.4.3 of the CIP INN-005-EXT. The presence of corneal edema, encapsulated bleb, hyphema, hypopyon, iris atrophy, pigment dispersion, pupillary irregularities, tube exposure and other slit lamp findings will be evaluated and noted.
Best Corrected Visual Acuity	Best Corrected Visual Acuity (BCVA) should be measured using Early Treatment of Diabetic Retinopathy Study (ETDRS) charts at 4 meters (13 feet and 1.5 inches, or 157.5 inches) in both eyes and reported in LogMAR units.
Visual Field	Visual fields are to be performed with a non-dilated pupil unless, in the opinion of the Investigator, the pupil is so miotic that dilation is required (e.g., < 3 mm). If possible, measurements should be performed using the same instrument that acquired the INN-005 study Screening measurements.

Confidential Page 27 of 32

Table 3: Safety Assessments (Continued)

Safety Measures	Note
Lens Status for Phakic Eyes	LOCS III classification system should be used to evaluate the lens for the presence of cataract for subjects with a phakic study eye.
Pachymetry	Three measurements are taken utilizing an electronic ultrasound pachymeter to determine central corneal thickness. If possible, measurements should be performed using the same instrument that acquired the INN-005 study Screening measurements.
Anterior Segment OCT	Anterior Segment Optical Coherence Tomography (OCT) should be performed on subjects who still have the PRESERFLO® MicroShunt device implanted, if equipment available.
Endothelial Cell Density	Central enthothelial cell density (ECD) images will be collected for study and fellow eyes. ECD can be taken before Anterior Segment OCT is completed. All readings will be conducted by the Corneal Image Analysis Reading Center.
Dilated Fundus Exam	The appearance of the optic disc, macula, vessels, and periphery should be evaluated. A measurement of vertical cup-to-disc ratio should be made.
Bleb and Seidel Test	A Seidel test will be used to detect ocular perforation or a wound leak.
Manifest Refraction	Manifest refraction will be performed.
Diplopia	Subjects will be assessed for diplopia.
Ocular Motility Test	Ocular motility will be evaluated.

The safety-related measures collected in this study include ocular AEs, SAEs, Best Corrected Visual Acuity (BCVA), visual field, results of slit lamp, fundus examination, specular microscopy (endothelial cell density), lens evaluation classification system (LOCS III), and the incidence of surgical complications and adverse events (AEs), Anterior Segment OCT, Bleb and Seidel test, manifest refraction, diplopia, and ocular motility. All safety-related measures are collected only on the study eye, except AEs, SAEs and Endothelial Cell Density, which will be collected for both eyes.

9.2. Analysis of Safety Outcomes

All the safety-related outcome measures will be summarized descriptively for each cohort of the Enrolled population by study group.

9.2.1. Analysis of Primary Safety Outcome Measure

The analysis of the primary safety outcome measure, the incidence of sight-threatening AEs, will be performed on the Enrolled population. The number and percentage of subjects who experienced any sight-threatening AEs, and the 95% exact (Clopper-Pearson) confidence intervals of the incidence rate will be computed for each study group at each study follow-up visit. Additionally, the rate differences and their corresponding 95% exact (Chan-Zhang) confidence interval of the rate differences will also be provided.

Confidential Page 28 of 32

The data listing of subjects who experienced at least one sight-threatening AE will be provided.

9.2.2. Analysis of Secondary Safety Outcome Measures

9.2.2.1. Adverse Events

Subjects with any ocular AEs, SAEs, and UADEs will be tabulated and summarized by type of AEs for each study group. Ocular AE summaries (i.e., the number and percentage of subjects reporting to at least one AE) will also be provided for ocular AEs judged to be device- or procedure-related.

AEs, SAEs, and UADEs, if any, will be listed separately.

9.2.2.2. Best-Corrected Visual Acuity (BCVA)

Best corrected visual acuity (BCVA), changes and percent changes in BCVA from the INN-005 study Screening, collected in both INN-005 and INN-005-EXT study, will be summarized descriptively by study group and study follow-up visit. Number and percentages of subjects with a BCVA AE, (a BCVA loss of 2 lines, i.e., 10 ETDRS letters, or more from the INN-005 study Screening on 2 consecutive standard follow-ups 90 days or more after the original procedure will be provided for each study group at each study follow-up visit. However, a loss of BCVA in conjunction with posterior capsule opacification, followed by Nd:YAG capsulotomy and improvement of BCVA will not be considered as an adverse event.

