9.4.1. BCVA (ETDRS)

Best Corrected Visual Acuity (BCVA) should be measured using Early Treatment of Diabetic Retinopathy Study (ETDRS) charts at 4 meters (13 feet and 1.5 inches, or 157.5 inches) in both eyes and reported in LogMAR units.

Visual acuity testing should precede slit lamp examination, intraocular pressure measurement, the administration of topical anesthetic agents, or any examination requiring contact with the anterior segment.

The visual acuity chart must be retro-illuminated ("back-lit"). The standard chart requires a distance from subject to chart of 4 meters. Ideally, the subject should be seated. Sites should refer to the instructions on the commercial ETDRS charts and the Visual Acuity Testing Manual, provided as part of the INN-005 study.

The subject should attempt to read each letter, line by line, left to right, beginning with line 1 at the top of the chart (20/200 line). The subjects should be told that the chart has letters only, no numbers. If the subject reads a number, he or she should be reminded that the chart contains no numbers, and the examiner should then request a letter in lieu of the number. The subjects should be asked to read slowly, about one letter per second, so as to achieve the best identification of each letter. He/she is not to proceed to the next letter until he/she has given a definite response.

In order to provide standardized and well-controlled assessment of visual acuity during the study, all visual acuity assessments for a subject must be performed consistently (e.g., the same lighting conditions, viewing distance, etc.) during the entire study.

The following steps will be used for LogMAR scoring:

- 1. The examiner records each letter identified correctly by circling the corresponding letter on the Distance Visual Acuity Worksheet to be provided to the investigative sites.
- 2. Letters read incorrectly or not read at all are not marked on the form.
- 3. Each letter read correctly is scored as one point.
- 4. The total score for each eye is recorded on the worksheet after testing is completed.

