9.6.5. Subject Study Completion

Subjects complete and exit the study when they have completed the Month 60 Follow-Up Visit. Subjects will then continue to be followed by their primary health care provider as required. A subject will also be exited from the study in the following instances:

- Subject is Lost-to-Follow-Up. Multiple attempts must be made to contact the subject before
 withdrawing them from the study. These attempts must be documented in the appropriate CRF.
 For those subjects who cannot be reached, at least three (3) telephone call attempts should be
 made. If there is still no response, a registered letter shall be sent to the last known address on
 file for the subject in an attempt to make contact. If there is still no response, the subject will be
 considered Lost-to-Follow-up unless there is subsequent communication by the subject.
- Subject withdraws participation from the study or is withdrawn from the study by the Investigator
- Subject expiration

All subjects enrolled in the clinical study (including those withdrawn from the clinical study or who are Lost-to-Follow-Up) will be accounted for and documented. If a subject withdraws from the clinical study, the reason(s) for withdrawal shall be reported on the appropriate CRF. If such withdrawal is due to problems related to the PRESERFLO® MicroShunt, the Investigator will ask for the subject's permission to follow his or her status/condition outside of the clinical study.

Subjects may withdraw from the study at any time, with or without reason, and without prejudice to further treatment. The Investigator may withdraw a subject if, in his/her clinical judgement, it is in the best interest of the subject or if the subject cannot comply with the protocol. The Sponsor must be notified of all withdrawals.

If a subject withdraws their consent to participate, or the Investigator decides to withdraw the subject, it will be documented in the appropriate CRF. No additional data may be collected after the point at which a subject has been withdrawn from the study or withdraws consent. Withdrawn subjects will not be replaced. All open Adverse Events should be closed or documented as ongoing. Data collected up to the point of subject withdrawal may still be used.

10. Risks and Benefits

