13.1. Anticipated Adverse Events

Anticipated adverse events include those that might reasonably be expected to occur in this study because they are associated with glaucoma, glaucoma surgery, and/or prior cataract surgical procedures. Specific examples of anticipated adverse events include:

- Hypotony; defined as IOP <6mmHg.
- 2. Increased intraocular pressure requiring medical or surgical intervention; Increased intraocular pressure will be considered an adverse event if a subject has an IOP higher than the preoperative medicated screening pressure or 21mmHg, whichever is lower. At this IOP level, the Investigator will intervene either physically or with the addition of glaucoma medication. There may also be cases where intervention for increased IOP is done at a lower IOP level than stated above because of other patient-related factors; these will also be adverse events.
- 3. Decrease of BCVA; BCVA decreases of 2 lines or more should not be reported as adverse events until they occur at two consecutive visits unless surgical or medical intervention is required. If the first decrease is noted at the Study Exit Visit, the subject will be exited and not brought back. In this case, the decrease will not be documented as an adverse event. (Note: a loss of BCVA in conjunction with posterior capsular opacification, followed by Nd:YAG capsulotomy and improvement of BCVA, is not considered an adverse event.)

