8.1.3. Change (and Percent Change) from Screening

The change and the percent change from screening in a measure at a post-operative follow-up visit will be derived as:

- Change = (Score at the follow-up Visit) W(Screening Score)
- Percent Change from Screening = 100 × Change / (Screening Score)

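### Percent change in BCVA is planned, but the only stated reporting scale is logMAR, where the ratio has no value at 0 and changes sign below it

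*SAP*

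**What the plan says.** **Percent change.** SAP 9.2.2.2 summarises BCVA and "changes and percent changes in BCVA from the INN-005 study Screening" by study group and visit. SAP 8.1.3 gives one formula for every measure, beginning "Percent Change from Screening = 100" and then multiplying by the change over the screening score. It has no rule for a screening score of zero or below.

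**Scale.** SAP 9.1.2 (Table 3) says BCVA is measured "in both eyes and reported in LogMAR units", and protocol 9.4.1 says the same. Letters appear in two other places. Protocol 9.4.1 lists steps for logMAR scoring, one of which is "Each letter read correctly is scored as one point", with reading "beginning with line 1 at the top of the chart (20/200 line". SAP 9.2.2.2 equates two lines with 10 letters when it defines a BCVA adverse event. Neither place names letters as the scale for the change summaries.

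**Counting losses.** The BCVA adverse-event row in SAP 9.2.2.2 requires a loss of at least 10 letters "on 2 consecutive standard follow-ups 90 days or more after the original procedure". Protocol 13.1 has the matching reporting rule: decreases of two lines or more "should not be reported as adverse events until they occur at two consecutive visits unless surgical or medical intervention is required". It adds that a decrease first noted at the exit visit is not recorded as an adverse event and the subject does not return. Protocol 9.6.5 sets the exit: "Subjects complete and exit the study when they have completed the Month 60 Follow-Up Visit".

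**The concern.** A percent change needs a scale with a true zero and values on one side of it. LogMAR has neither: its zero is an ordinary level of good vision, and eyes fall on both sides. Dividing by the screening value turns equal losses into very different numbers, some with the opposite sign, and some eyes drop out because the denominator is zero. Two arms with identical losses could then show different mean percent changes, for a reason unrelated to treatment.

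The second matter is smaller. The study describes safety through five years, yet the only planned count of two-line losses needs two consecutive visits, and Month 60 is the last. A loss first seen there cannot be confirmed, so it cannot enter that row.

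**Working it through.** There is no power, sample-size or alpha figure to reproduce. The check applies the plan's own formula and then traces the two-visit rule.

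**Inputs from the documents**
- Percent change = 100 × (follow-up − screening) / screening (SAP 8.1.3).
- 2 lines = 10 letters (SAP 9.2.2.2), so 5 letters per line.
- Line 1 of the chart = 20/200 (protocol 9.4.1).

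**Assumption.** 0.1 logMAR per line, so 0.02 per letter and 10 letters = 0.20. A fully read line 1 (5 letters) is logMAR 1.0, so logMAR = 1.1 − 0.02 × letters, and logMAR 0 is 55 letters on this count.

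**Step 1. One loss, different screening values.** Every eye loses 10 letters.

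| Screening logMAR | Letters | Percent change, logMAR: 100 × 0.20 / screening | Percent change, letters: 100 × (−10) / letters |
|---|---|---|---|
| 0.30 | 40 | +67% | −25% |
| 0.10 | 50 | +200% | −20% |
| 0.02 | 54 | +1000% | −19% |
| 0 | 55 | undefined | −18% |
| −0.02 | 56 | −1000% | −18% |
| −0.10 | 60 | −200% | −17% |

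The absolute change is +0.20 logMAR in every row.

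**Step 2. Effect on a mean.** Take five eyes screening at 0.30, 0.20, 0.10, −0.02 and −0.10, each worsening by 0.20. The percent changes are +66.7, +100, +200, −1000 and −200. Their sum is −833.3, so the mean is −167%. The median is +67%.

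**Step 3. Larger groups.** The documents do not give the screening distribution, so three normal distributions (rounded to whole letters) are assumed. For each, 20,000 groups of 100 eyes were simulated. Every eye loses exactly 10 letters, and zeros are dropped. Ranges are the 2.5th to 97.5th percentiles across groups.

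| Assumed mean / SD | Share at or below 0 | Group mean percent change | Group median percent change |
|---|---|---|---|
| 0.20 / 0.10 | 3% | +90% to +160% | +83% to +111% |
| 0.10 / 0.15 | 27% | about +3% to +147% | +77% to +125% |
| 0.05 / 0.20 | 42% | −46% to +93% | +33% to +91% |

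The absolute mean change is +0.20 in every group. The planned minimum and maximum are set by the eyes closest to 0.

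**Step 4. The two-visit rule.** With loss flags at Months 24, 36, 48 and 60:
- (0, 0, 0, 1) is not counted.
- (0, 0, 1, 1) is counted.
- A subject who enrols after the Month 36 and 48 windows, which protocol 5.1 allows, with no loss at Month 24 and a loss at Month 60, is not counted.

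**Step 5. Noise cost of a single-visit count.** Suppose vision is truly unchanged and the screening-to-visit difference is normal with an SD of 4 to 7 letters (assumed). A loss of 10 or more whole letters then has probability P(Z > 9.5/SD): 9.5/4 = 2.375 gives 0.9%, and 9.5/7 = 1.357 gives 8.7%. For two visits sharing one screening value (correlation 0.5, assumed) the figures are 0.11% and 2.7%.

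**The case against.** **Letters may be what is analysed.** The scoring steps in protocol 9.4.1 end in a letter total with no conversion to logMAR, and SAP 9.2.2.2 defines a loss in letters. On a letter score the percent change behaves well, as Step 1 shows. This stands as a reason to name the scale. It does not rescue the current text: the letter count is listed as part of logMAR scoring, and logMAR is the only scale on which either document says BCVA is reported.

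**The median is also planned.** SAP section 5 reports the median, and in Step 3 it stays positive throughout. This stands. The firm conclusion concerns the mean and the extremes; the median is distorted less.

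**The Month 60 rule is deliberate.** Protocol 13.1 states it openly, and confirmation protects against noise. This stands too, so the missing count is not an error. A reader might infer that Month 60 losses are lost to the safety record. The documents do not support that:
- The values enter the BCVA change summaries and the individual listings (SAP section 5).
- A diagnosed cause, such as cataract progression or macular edema, can be tabulated under its own term (protocol 13.2, SAP 9.2.2.1).
- Lens worsening has its own per-visit count (SAP 9.2.2.4).
- Protocol 13.1 lets a loss that needs intervention be reported without confirmation.

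Nor does every new loss in a late enrollee go unseen until Month 60. Ocular events between Month 24 and consent that needed intervention are collected at enrollment (protocol 9.3.3 and section 13). Events found at unscheduled visits are recorded as well (protocol 9.6.4).

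**Conclusion.** The percent-change summary is wrong as written. On the stated scale it is undefined at 0 and reverses sign below 0, and its mean cannot be interpreted when some eyes screen at, near or below 0. How many do is unknown; the 3% to 42% in Step 3 rests on assumed distributions. The table in Step 1 needs only the SAP formula and 0.02 logMAR per letter.

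The Month 60 matter is an optional improvement. The accurate statement is narrow: no planned table counts a two-line loss as such when it is first seen at Month 60 and needs no intervention. SAP 9.2.2.2 also omits the intervention exemption in protocol 13.1, so the two should be reconciled.

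A reader might go further and doubt the BCVA safety results as a whole. That does not follow. The absolute change is planned and sound, the analyses are descriptive with no hypotheses, and the primary outcome, sight-threatening adverse events, does not use this statistic.

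**What to change.** 1. In SAP 9.2.2.2, name the scale on which BCVA is analysed.
2. Delete percent change for BCVA and report the absolute change already planned. SAP 9.2.2.6 already does this for visual field mean deviation, another signed scale. Percent change could stay only if the SAP states that a letter score is analysed.
3. State in SAP 9.2.2.2 whether the intervention exemption in protocol 13.1 applies to the BCVA adverse-event row.
4. Optional: keep the confirmed row as the main one and add beside it the number and percentage with a loss of 10 letters or more from screening at each visit, labelled unconfirmed.

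The cost is SAP wording and, for item 4, one table row. All values are already collected and no visit is added. On logMAR, deleting percent change loses nothing usable. The price of item 4 is noise: about 0.9% to 8.7% of unchanged eyes would appear at a single visit under the assumed SDs, which is why the row needs its label and the confirmed row should lead.

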9.6.2. Month 36, 48, and 60 Follow-Up Visit

All Follow-Up Visit Assessments are identical for the Month 36, Month 48, and Month 60 Visits.

The Month 36, 48, and 60 Follow-Up Visits shall be conducted per the following windows, calculated from the subject's date of surgery in the INN-005 study:

Follow-Up Visit	Visit Window
Month 36	Day 1080 ± 90 days
Month 48	Day 1440 ± 90 days
Month 60	Day 1800 ± 90 days

The following study assessments are to be performed at all 3 Follow-Up Visits:

- Glaucoma Medications
- 2. Concomitant (ocular) Medications
- 3. Adverse Event Assessment

The following study procedures are to be performed at all 3 Follow-Up Visits:

- 1. Manifest Refraction
- 2. BCVA (ETDRS)
- 3. Visual Field
- 4. Slit Lamp Exam
- 5. IOP
- 6. Pachymetry
- 7. Anterior Segment OCT
- 8. Endothelial Cell Density
- 9. Lens Status for Phakic Eyes
- 10. Dilated Fundus Exam (including Vertical C/D Ratio)
- 11. Bleb and Seidel Test
- 12. Diplopia
- 13. Motility

The following additional study procedure is to be performed at the Month 60 Follow-Up Visit, if subject has signed the Consent Addendum:

Gonioscopy (for MicroShunt subjects who still have device implanted)

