13.2. Post-operative Anticipated Adverse Events

- Anterior chamber puncture
- Aqueous humor misdirection (malignant glaucoma)
- Blebitis
- Bleb leak
- Bleb related complications e.g. cystic bleb, flat bleb
- Cataract progression
- Choroidal effusion/detachment
- Choroidal hemorrhage
- Chronic iritis
- Chronic pain

- · Clinically significant corneal damage
- Clinically significant iris damage
- Confirmed worsening in the visual field of mean deviation (MD) of ≥2.5 dB compared to the MD
 used to determine subject eligibility (confirmed on at least 2 out of 3 visual field tests performed
 after 3 months post procedure)
- Conjunctival dehiscence
- Conjunctival dissection
- Corneal abrasion
- Corneal edema
- Diplopia
- Device malfunction
- Encapsulated bleb
- Endophthalmitis
- Erosion of the device through the conjunctiva
- Event requiring unplanned glaucoma-related ocular surgical intervention
- Event requiring unplanned surgical intervention for reason other than glaucoma
- · Flat anterior chamber
- Hyphema at any time (including microhyphema)
- Hypotony (IOP<6mmHg at any time)
- Hypotony maculopathy
- Implant migration
- Increase in C/D ratio of ≥0.3 units on slit lamp biomicroscopic examination
- Increased IOP requiring treatment
- Leakage of wound site
- Loss of light perception
- Loss of 2 lines or more of BCVA on 2 consecutive follow-up visits
 (Note: a loss of BCVA in conjunction with posterior capsule opacification, followed by Nd:YAG capsulotomy and improvement of BCVA, is not considered an adverse event)
- Macular edema
- Optic disc hemorrhage
- Posterior capsule opacification
- Proptosis
- Ptosis
- Pupillary block
- Retinal complication (dialysis, flap tears, detachment, decompression or proliferative retinopathy)
- Shallow anterior chamber
- Strabismus
- Subconjunctival bleeding at any time
- Suture abscess or other local infection
- Tube obstruction, partial or complete, regardless of how long the obstruction is present
- Tube touching cornea
- Tube touching iris
- · Use of a viscoelastic to limit aqueous flow
- Vitreous hemorrhage

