3.4. Visits and Assessments

Subjects enrolled in this study will be required to complete up to three (3) annual follow-up visits through post-operative Month 60 Follow-Up Visit and may therefore be in the study for up to three (3) years following completion of their Month 24 Follow-Up Visit in the INN-005 clinical study. Assessments at each visit and the time/visit window for each follow-up assessment are specified in the Assessment Schedule (Table 1). Essentially, most of the study procedures are the same as those performed as part of the INN-005 study, the differences are listed as follows:

Study Assessment	INN-005 Study (Month 12 and 24)	INN-005-EXT Study (Month 36, 48, and 60)	Comments
IOP	Diurnal	Standard	INN-005: Diurnal IOP INN-005-EXT: Standard IOP
Anterior Segment OCT	Not performed	Performed	INN-005-EXT: An optional assessment only performed for subjects with device still implanted
Adverse Event Assessment	All AEs	All SAEs; Ocular AEs	INN-005: All AEs collected INN-005-EXT: All ocular AEs in study & fellow eye and all SAEs (ocular and non-ocular) will be collected. Non-serious, non-ocular AEs will not be collected.
Ocular QOL Questionnaire	Performed	Not performed	
General Health Questionnaire	Performed	Not performed	

Confidential Page 11 of 32

 Table 1:
 Assessment Schedule

			Follow-Up Evaluation						
Activities	Enrollmenta		Month 36 Visit (Day 1080 +/-90 days)		Month 48 Visit (Day 1440 +/-90 days)		Month 60 Visit (Day 1800 +/-90 days)		Un- scheduled Visit
	SE	FE	SE	FE	SE	FE	SE	FE	
Study Assessments									
1. Informed Consent & Research Authorization	X								
2. Eligibility Assessment	X								
3. Medical/Surgical History ^b	X	X							go cd
4. Glaucoma Medications ^{c,e}	X	X	X	X	X	X	X	X	SOC^d
5. Concomitant (ocular) Medications ^{c,e}	X	X	X	X	X	X	X	X	
6. Adverse Event Assessment ^e	X	X	X	X	X	X	X	X	
Study Procedures ^f	•			•			•	•	
1. Manifest Refraction			X		X		X		
2. BCVA (ETDRS)			X		X		X		
3. Visual Field			X		X		X		
4. Slit Lamp Exam			X		X		X		
5. IOP			X		X		X		
6. Pachymetry			X		X		X		SOC^d
7. Anterior Segment OCT ^g			X		X		X		
8. Endothelial Cell Density			X	X	X	X	X	X	
9. Lens Status for Phakic Eyes ^h			X		X		X		
10. Dilated Fundus Exam (incl. Vertical C/D Ratio)			X		X		X		

Confidential Page 12 of 32

			Follow-Up Evaluation						
Activities	Enrollmenta		Month 36 Visit (Day 1080 +/-90 days)		Month 48 Visit (Day 1440 +/-90 days)		Month 60 Visit (Day 1800 +/-90 days)		Un- scheduled Visit
	SE	FE	SE	FE	SE	FE	SE	FE	

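### A 2-line BCVA loss that is treated and recovers before the next standard visit is an AE under Protocol 13.1 but is not counted in the SAP's BCVA AE rate

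*SAP*

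**What the plan says.** Three places define a BCVA loss of 2 lines or more as an adverse event.

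- **Protocol 13.1 (Anticipated Adverse Events), item 3.** Such decreases "should not be reported as adverse events until they occur at two consecutive visits unless surgical or medical intervention is required". By implication, a loss that needs intervention is reportable the first time it is seen. The same item covers the end of the study: "If the first decrease is noted at the Study Exit Visit, the subject will be exited and not brought back", and that decrease is not recorded as an AE.
- **Protocol 13.2 (Post-operative Anticipated Adverse Events).** The list entry is "Loss of 2 lines or more of BCVA on 2 consecutive follow-up visits". It has no intervention route.
- **SAP 9.2.2.2 (BCVA).** The number and percentage of subjects with a BCVA AE is reported by group and visit. The event is "a BCVA loss of 2 lines, i.e., 10 ETDRS letters, or more from the INN-005 study Screening on 2 consecutive standard follow-ups", at least 90 days after the procedure. The only carve-out is a loss linked to posterior capsule opacification that improves after Nd:YAG capsulotomy. It has no intervention route either.

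SAP 9.1.1.1 points to both 13.1 and 13.2 for the anticipated AEs and does not say which governs. SAP 9.2.2.1 separately tabulates ocular AEs by type and lists AEs.

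**The concern.** One event name carries two case definitions. An investigator following 13.1 completes an AE form for a treated loss at once. The programmer following SAP 9.2.2.2 counts a subject only if the loss is present at two standard follow-ups in a row. The BCVA table and the ocular AE table can then disagree, and the plan gives no rule for reconciling them.

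The wide spacing of extension visits makes this more than a wording issue, because a treatable loss has ample time to arise, be treated and resolve between two scheduled measurements. The documents expect such losses. Protocol 11.2 describes intervention for hypotony that reduces BCVA by two or more lines, and Protocol 9.6.3 anticipates cataract surgery during follow-up.

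At stake is a rate labelled as an AE rate, in a study whose objective is long-term safety, that leaves out some events the protocol calls AEs.

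**Working it through.** The documents state no expected rate, sample size or power for this measure, so there is no plan figure to reproduce. The check compares the three rules and works out the visit spacing.

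**1. Visit spacing.** SAP 3.4 states: "Subjects enrolled in this study will be required to complete up to three (3) annual follow-up visits through post-operative Month 60". Protocol 9.6.2 gives Month 36 as "Day 1080 ± 90 days", Month 48 as "Day 1440 ± 90 days", and Month 60 as Day 1800 with the same 90-day tolerance.

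- Month 36 window: 1080 − 90 = 990 to 1080 + 90 = 1170
- Month 48 window: 1440 − 90 = 1350 to 1440 + 90 = 1530
- Month 60 window: 1800 − 90 = 1710 to 1800 + 90 = 1890

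Shortest gap = next window opens − previous window closes. Longest gap = next window closes − previous window opens.

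| Pair | Nominal | Shortest | Longest |
|---|---|---|---|
| Month 36 to 48 | 1440 − 1080 = 360 | 1350 − 1170 = 180 | 1530 − 990 = 540 |
| Month 48 to 60 | 1800 − 1440 = 360 | 1710 − 1530 = 180 | 1890 − 1350 = 540 |

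**2. The same eye under each rule.**

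| Course of a loss of 2 lines or more | Protocol 13.1 | Protocol 13.2 and SAP 9.2.2.2 |
|---|---|---|
| Present at two consecutive scheduled visits, treated or not | AE | Counted |
| Seen at Month 36 or 48, treated, recovered by the next scheduled visit | AE | Not counted |
| Seen and treated only between scheduled visits | AE | Not counted if standard excludes unscheduled visits |
| Seen once, untreated, recovered | Not an AE | Not counted |
| First seen at the exit visit, untreated | Not an AE | Not counted, unless an earlier visit forms the pair |

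The rules part in the second and third rows. Taking scheduled visits as the consecutive ones, every eye that meets the SAP rule also meets 13.1. The SAP count can therefore equal the 13.1 count or fall below it.

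**3. How much falls out.** If T treated losses are first seen at Month 36 or 48 and a share q is still 2 lines or more at the next scheduled visit, the SAP counts T × q and omits T × (1 − q). The documents give neither T nor q. With an assumed T = 20:

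| q | Counted | Omitted |
|---|---|---|
| 0 | 0 | 20 |
| 0.25 | 5 | 15 |
| 0.50 | 10 | 10 |
| 0.75 | 15 | 5 |
| 1 | 20 | 0 |

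The range runs from all to none, so this shows the mechanism and is not an estimate.

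**4. Which visits can pair.** SAP 9.2.2.2 does not define a standard follow-up. By contrast, SAP 8.1.5 states the visit type for each of its two-visit failure criteria: annual scheduled visits for loss of light perception, scheduled or unscheduled visits for low IOP. Under Protocol 5.1 a subject may enrol after the Month 36 and Month 48 windows have passed. Such a subject has only Month 60 in the extension and cannot form a pair there. SAP 9.2.2.2 summarises BCVA from both studies but does not say whether INN-005 Month 24 can be the first visit of a pair.

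**The case against.** The strongest reply is that the SAP follows Protocol 13.2 closely: the same two-visit rule, the same Nd:YAG exception and no intervention route. That is correct. The conflict starts inside the protocol, between 13.1 and 13.2, and the SAP carries one side of it forward.

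A reader might infer that treated losses vanish from the results. The documents do not support that. The SAP rule takes no account of treatment, so a treated loss still present at the next standard visit is counted. Omitted losses remain in the ocular AE tabulation and listings, and a loss measured at a scheduled visit enters the BCVA change summaries.

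A reader might also infer that a listed secondary outcome is compromised. The outcome listed in SAP 2.2.2 is change in BCVA, which 9.2.2.2 delivers. The 2-line rate is an additional summary. Nor does anything in the documents show that treated and recovered losses differ between arms, so a claim of bias in the comparison would rest wholly on assumed inputs.

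Two further points stand and shape the fix. Protocol 14.1 asks for the diagnosis when it is known, so a treated loss may be recorded as, for example, cataract progression or hypotony maculopathy. The two tables then need not clash under one label, and finding these eyes needs a linking rule. Also, the study is open-label and intervention is discretionary, so merging an intervention trigger into a measurement-based rate would bring in treatment-aware judgement. That argues for separate rows.

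None of this removes the mismatch. A rate called BCVA AE still leaves out events that 13.1 makes AEs.

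**Conclusion.** The point holds as a definitional mismatch with a one-directional effect on one rate. Losses treated and recovered before the next standard visit, a gap of 180 to 540 days in the extension, are AEs under Protocol 13.1 and are absent from the SAP's BCVA AE rate. The rate therefore equals or understates the 13.1 event. This rests on reading 13.1 as making a treated loss reportable at first occurrence. The third row of the comparison also assumes that standard follow-ups exclude unscheduled visits.

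The size of the shortfall and any imbalance between arms cannot be determined from the documents. The study is descriptive, with no hypotheses and no labelling claims, and the events are reported elsewhere. The consequence is a mislabelled and possibly low supplementary safety rate, not a loss of safety data. It merits correction because the remedy is cheap and uses data already collected.

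**What to change.** Reconcile Protocol 13.1, Protocol 13.2 and SAP 9.2.2.2 so that one definition governs. In SAP 9.2.2.2:

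1. Label the existing two-visit measure *confirmed BCVA loss of 2 lines or more*.
2. Add a separate row for study eyes with a loss of 2 lines (10 letters) or more from INN-005 Screening at one visit, where the AE form records surgical or medical intervention for it. Link the eye to the AE even when the AE is coded under the causal diagnosis, and state the linking rule before database lock.
3. Add a combined row that matches 13.1, counting each eye once.
4. Keep the Nd:YAG exception in all rows.
5. Define standard follow-up. State whether unscheduled visits and the INN-005 Month 24 visit can form part of a consecutive pair, and how subjects with a single extension visit are handled.

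The cost is SAP and protocol wording, slight extra programming, and a review to link AE forms to BCVA readings. The confirmed-loss row stays purely measurement-based. The combined rate may be higher than the one now planned.
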